### Study protocol

This study aims to evaluate methods for optimizing hip exoskeleton assistance to minimize gait variability. Optimization is guided by gait variability measurements quantified by the largest Lyapunov Exponent (LyE). The rationale is that this variability exponent provides a measure to track improvements in gait stability during different assistance conditions. The study is an interventional basic science study without blinding since it is not feasible to blind participants to the presence or absence of the exoskeleton or the different assistance conditions.

The protocol is performed at the Department of Biomechanics at the University of Nebraska at Omaha (UNO). Before the experiments, participants complete a health questionnaire and are fitted with an exoskeleton suit. Participants first start with a habituation session to get used to walking with the exoskeleton. Next, they proceed to the data collection session. During the optimization trials, healthy controls walk up to 20 minutes; patients with PAD walk 10x1 minutes with at least 2 minutes of rest. An algorithm prescribes the assistance profiles of the exoskeleton suit. After the optimization trials, participants will perform validation tests during which they repeat walking in the different exoskeleton and no-exoskeleton conditions (four trials of a maximum of 5 minutes for the healthy controls and two trials of a maximum of 6 minutes or until claudication onset for patients with PAD). The entire experiment will take no more than 1 hour for session 1 and 3 hours for session 2.

Hip extension and hip flexion assistance are measured using load cells (Futek Advanced Sensor Technology, Irvine, CA, USA). These load cells are connected to an exoskeleton input/output system (HuMoTech, Pittsburgh, PA, USA). To analyze the biomechanical responses to the exoskeleton assistance, three-dimensional movement data of all participants are recorded using a motion capture system (100 Hz, Vicon, Oxford, UK). The motion capture system is calibrated before data collection using a standard L-frame and a wand calibration method, following the manufacturer-recommended procedures. Reflective markers are placed on each participant's predefined anatomical landmarks according to a modified Helen Hayes marker set. Ground reaction forces are measured during walking using an instrumented force-treadmill (1000 Hz, Bertec, Columbus, OH). To remove unrealistic noise, all biomechanical signals are smoothed using a digital low-pass Butterworth filter with a cutoff frequency of 10 Hz.

Inverse dynamics analyses are conducted on the filtered biomechanical data to calculate joint moments and joint powers. These calculations are carried out using Visual3D (C-Motion, Germantown, MD). From these analyses, sagittal plane joint angles are extracted for further evaluation. To determine the torque exerted by the exoskeleton suit on the participant's hip joint, the measured forces from the load cells are multiplied by a fixed moment arm length, assumed to be 10 centimeters. The biological component of the hip joint moments is calculated by subtracting the exoskeleton-generated torque from the total joint moment computed through inverse dynamics.

Heel strikes are determined from the vertical ground reaction force signals using a threshold-based algorithm. Stride-segmented data are subsequently organized into a matrix data format within MATLAB software (MathWorks, Natick, MA, USA). Additionally, peak hip extension and flexion assistance timings are identified from the exosuit moment signals using a peak-detection algorithm. These timings are then expressed as percentages of the duration of each stride.

The primary outcome measures of this study include the peak extension timing and peak flexion timing provided by the exoskeleton suit, the time required for convergence of the optimization algorithm, and the largest Lyapunov Exponent (LyE), which is calculated as the average derived from leg joint angles.

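### One assumed 10 cm moment arm leaves the biological hip moment exposed to an error that arises only in the exoskeleton conditions and is neither measured nor bounded

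*Combined protocol and SAP*

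**What the plan says.** All the relevant text on processing is in the Study protocol section of the combined document.

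- **Torque.** To get exoskeleton torque at the hip, "the measured forces from the load cells are multiplied by a fixed moment arm length, assumed to be 10 centimeters". One value is given. It is not separated by participant or by direction (flexion or extension).
- **Biological moment.** "The biological component of the hip joint moments is calculated by subtracting the exoskeleton-generated torque from the total joint moment computed through inverse dynamics".
- **Conditions.** In the validation tests "they repeat walking in the different exoskeleton and no-exoskeleton conditions".
- **Primary outcomes.** "The primary outcome measures of this study include the peak extension timing and peak flexion timing provided by the exoskeleton suit". The list continues with convergence time and the Lyapunov exponent (LyE), "which is calculated as the average derived from leg joint angles". Biological hip moment is not on it.
- **Timing.** "peak hip extension and flexion assistance timings are identified from the exosuit moment signals using a peak-detection algorithm".

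The Statistical analysis plan section promises mean and SD by condition for the biomechanical variables, moments and powers included. It names repeated-measures ANOVA for comparing conditions but does not say which variables enter it. Nowhere does the document describe an individual arm measurement, a check of the 10 cm value, or a sensitivity range.

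**The concern.** The distance from the hip joint centre to the line of pull depends on body size and need not be the same in front (flexion) as behind (extension). A single assumed number stands in for all of this and feeds straight into a subtraction.

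An error common to all conditions would largely drop out of a within-person comparison. This one does not. It is proportional to suit force, so it is present when the suit pulls and absent when there is no suit. It also fails to cancel between two assistance conditions whose forces differ.

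At stake is the reading of the biological hip moment by condition. An apparent reduction with the suit would mix a real change in the wearer's own moment with an artefact of the assumed arm. As the plan stands, a reader could not tell how much is which.

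**Working it through.** The plan states no figure to reproduce, so the check is error algebra followed by a stated range.

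**Inputs.** From the document: arm 0.10 m; biological moment = total moment − torque; exoskeleton and no-exoskeleton conditions. Assumed, because the document gives neither: suit force F of 50, 100 and 200 N; true arm r from 8 to 12 cm; between-person SD of the arm 1 cm.

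**Step 1: error for one participant.** Moments are taken as positive in the direction of assistance.

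- Computed: M_total − 0.10F
- True: M_total − rF
- Error (computed − true): (r − 0.10) × F

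With no exoskeleton, F = 0 and the error is exactly 0, whatever r is. Between two assistance conditions the error in the difference is (r − 0.10) × (F₁ − F₂), which vanishes only if the forces are equal.

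**Step 2: size.** As a share of computed torque the error is (r − 0.10)/0.10, which does not depend on force.

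| True arm | Error at 50 N | 100 N | 200 N | Share of computed torque |
|---|---|---|---|---|
| 8 cm | −1.0 Nm | −2.0 Nm | −4.0 Nm | −20% |
| 9 cm | −0.5 Nm | −1.0 Nm | −2.0 Nm | −10% |
| 10 cm | 0 | 0 | 0 | 0% |
| 11 cm | +0.5 Nm | +1.0 Nm | +2.0 Nm | +10% |
| 12 cm | +1.0 Nm | +2.0 Nm | +4.0 Nm | +20% |
| No exoskeleton | 0 | 0 | 0 | – |

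A negative error makes the biological moment too low and so overstates offloading. A positive error understates it.

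**Step 3: group level.** The mean error in the exoskeleton versus no-exoskeleton contrast is E[(r − 0.10)F]. It is zero when the force-weighted mean arm is 10 cm, and otherwise not. At F = 100 N with an arm SD of 1 cm:

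- mean arm 9 cm: mean error 100 × (−0.01) = −1 Nm
- mean arm 10 cm: mean error 0
- mean arm 11 cm: mean error 100 × 0.01 = +1 Nm

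In all three cases the SD of the error is 100 × 0.01 = 1 Nm. If arm error is unrelated to the true biological moment, this adds 1² = 1 Nm² to the between-person variance in the exoskeleton condition and nothing without the suit.

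**Step 4: reach into the primary outcomes.** LyE is built from joint angles, so no arm enters. Convergence is judged by when the optimal settings stop changing, and no arm is named there. For timing, c × F(t) peaks at the same instant as F(t) for any positive constant c. In a numerical example, arms of 8, 10 and 12 cm all put the peak at 20.0% of stride. A wrong constant therefore cannot move the computed peak timings.

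**The case against.** The strongest reply is that this is an openly declared simplification affecting a peripheral quantity. The plan itself calls the 10 cm an assumption. The aim is to reduce gait variability, biological hip moment is not a listed primary outcome, and the only analysis named for moments is mean and SD. All of that stands, and it limits the importance of the point. It does not remove it: the moments will be reported by condition, the ANOVA is not restricted to the primary outcomes, and nothing in the document lets a reader judge the effect of the assumption.

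Three stronger readings are tempting, and the document does not support them.

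- **The contrast is biased.** Step 3 shows that mean bias requires a force-weighted mean arm other than 10 cm. The document gives neither arms nor forces, so bias is possible but not shown.
- **The primary timing outcomes are compromised.** Because the arm is constant, the moment peak is the force peak. The true torque peak would differ only if the arm varies within the stride. Under an assumed 20% change in arm across a half-sine pulse lasting 40% of stride, the shift is about 0.005/(π/40)² = 0.8% of stride. Those inputs are not in the document, and the outcome is described as timing delivered by the suit, for which a force peak is a reasonable measure.
- **The error could pass for a difference between PAD patients and controls.** That would need arms or forces to differ by group. The document gives no body-size data and names no between-group test.

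**Conclusion.** The point holds in limited form. The comparison of biological hip moment between exoskeleton and no-exoskeleton walking is exposed to a non-cancelling error of unknown sign and size.

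The scale is 0.01 Nm per newton for each centimetre of arm error: 1 Nm at an assumed 100 N, half that at 50 N, twice that at 200 N. The 10% of computed torque per centimetre holds at any force. Even if arms average exactly 10 cm, their scatter would inflate the reported SD in the exoskeleton conditions alone, provided arm error is unrelated to the true moment.

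The algebra follows from the plan's own formula. The forces, arms and arm SD are illustrations, not estimates. The consequence stops at biological hip moments and any joint powers computed from them; the listed primary outcomes are not put in doubt by a wrong value of the constant. It is worth correcting mainly because correction is cheap.

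**What to change.** 1. At the existing suit fitting, measure each participant's front (flexion) and back (extension) arm, and use these two values in place of 10 cm when converting force to torque.
2. Report biological hip moments by condition over a stated plausible range of arms, with the reason for the range. If data are already collected, this step alone is the fix and needs only re-analysis.
3. State in the Statistical analysis plan section whether biological hip moment enters the repeated-measures ANOVA.

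The cost is two short measurements per participant and a small change to the processing script. The measurements carry some error of their own, and the arm remains constant through the stride, so within-stride variation is not addressed. Tracking the line of pull frame by frame with extra markers would address it, but risks marker loss near the suit and is more than a non-primary quantity needs.

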### Statistical analysis plan

Variability is quantified based on the Lyapunov Exponent. First, the optimal time lag (Tau) necessary for state-space reconstruction is estimated through the Average Mutual Information (AMI) algorithm. Tau is determined at the first local minimum of the AMI curve. Next, the optimal embedding dimension, representing the minimum number of variables required to accurately reconstruct gait dynamics, is determined using the False Nearest Neighbor (FNN) method. With these parameters (Tau and embedding dimension), the original gait time series are reconstructed into a multi-dimensional state space. LyE is computed using Wolf's algorithm, which evaluates how quickly neighboring trajectories in state-space diverge from each other. LyE is calculated individually for the hip, knee, and ankle joints.

Repeated-measures Analysis of Variance (ANOVA) is used to compare differences between conditions. The convergence of the optimization algorithm is statistically assessed by determining the number of assistance conditions after which the optimal exoskeleton settings no longer change as the convergence criterion.

Descriptive statistics are computed for all biomechanical variables, including joint angles, moments, and powers. Specifically, each biomechanical variable's mean and standard deviation are calculated across all participants for each experimental condition. These descriptive statistical values are consistently reported as mean  $\pm$  standard deviation. A significance threshold for all statistical tests is set at a p-value of 0.05.

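### The two primary timing outcomes have no analysis of their own, and a mean ± SD of searched timings cannot show that a best timing exists or that it differs between people

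*Combined protocol and SAP*

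**What the plan says.** The Study protocol section lists four primary outcomes: two timings, time to convergence, and LyE. On the timings it says: "The primary outcome measures of this study include the peak extension timing and peak flexion timing provided by the exoskeleton suit". They are measured after the fact: "peak hip extension and flexion assistance timings are identified from the exosuit moment signals using a peak-detection algorithm". The assistance itself is not a free response of the participant: "An algorithm prescribes the assistance profiles of the exoskeleton suit", and the objective that guides the search is LyE. On the length of the search: "healthy controls walk up to 20 minutes; patients with PAD walk 10x1 minutes with at least 2 minutes of rest". Participants then repeat suit and no-suit walking in validation trials, four in controls and two in PAD. The suit settings used there are not named.

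The Statistical analysis plan has three analyses that could touch the timings:

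- a repeated-measures ANOVA between conditions, with neither outcome nor contrasts named;
- a convergence assessment, made by "determining the number of assistance conditions after which the optimal exoskeleton settings no longer change as the convergence criterion";
- a generic descriptive summary, in which "each biomechanical variable's mean and standard deviation are calculated across all participants for each experimental condition".

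None of these refers to peak timing.

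**The concern.** When an algorithm looks for the setting with the lowest LyE, it will return one whether or not LyE responds to timing. On a flat surface, any measurement error is enough to make one setting look best. If the chosen timings are then averaged over participants, the mean looks like the best timing and the SD looks like individuality, yet both can come from the error of locating a minimum.

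Two of the four listed primary outcomes are affected. Without an analysis that relates LyE to timing, they cannot support a statement about which timing lowers gait variability, or about whether the suit needs individual tuning.

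**Working it through.** The documents give no sample size, effect size, LyE error, timing range or algorithm, so there is no figure of the plan's own to reproduce. The check asks what the generic summaries would show if everyone shared one optimum, or if there were none.

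**From the documents:** two timings, LyE as the objective, ten 1-minute bouts in PAD (Study protocol); the generic methods (Statistical analysis plan).

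**Assumed:** one setting per PAD bout, so K = 10; each timing's range scaled to 0–1; settings placed at random; independent noise with SD 1; the chosen setting is the one with the lowest observed LyE. With e and f the extension and flexion timings and a common optimum at mid-range:

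LyE = D × [(e − 0.5)² + (f − 0.5)²] / 0.5 + N(0, 1)

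At a corner the bracket is 0.25 + 0.25 = 0.5, so D is the rise in LyE from centre to corner, in noise SDs.

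**Step 1: flat surface (D = 0).**
- The pick is one of ten exchangeable settings, so each timing is uniform: mean 0.50, SD = 1/√12 = 0.289. Simulation gave 0.288 and 0.289.
- The pick looks better than the average setting by 1.54 noise SDs, although the true gain is 0.
- If the optimum is the lowest value so far, its position is uniform on 1 to K. The mean position is (10 + 1)/2 = 5.5, and the best stops changing before the last setting with probability 1 − 1/10 = 90%. For K = 20 the figures are 10.5 and 95%. The convergence outcome therefore also returns a value when there is no effect.

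**Step 2: real effect, one optimum shared by everyone.** Simulated SD of the chosen timing, as a fraction of the range:

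| D | SD of lowest-LyE picks |
|---|---|
| 0 | 0.288 |
| 1 | 0.259 |
| 2 | 0.235 (0.234 in a second run) |
| 4 | 0.197 |

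Giving participants truly different optima (SD 0.10) at D = 2 moves the observed SD only from 0.235 to 0.242. The SD says little about real individuality.

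**Step 3: repeat the search in the same person.** This used a simpler model: one timing, K = 10 evenly spaced settings, depth measured from centre to edge. The between-person SD was 0.319, 0.239, 0.185 and 0.136 at depths 0, 1, 2 and 4. The correlation between two searches in the same person was 0.00 throughout, as it must be when people do not differ.

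**Step 4: how far modelling helps.** In that one-timing model, taking the minimum of a quadratic fitted to each person's ten values gave SDs of 0.402, 0.249, 0.115 and 0.034 at depths 0, 1, 2 and 4. The false spread shrinks quickly once there is signal, but on a flat curve it is larger than under the lowest-value rule.

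**Step 5: what the PAD validation trials can show.** If one of the two PAD trials is without the suit, the only contrast is suit versus no suit. Assume 10 patients and a standardized paired effect of wearing the suit of 0.8, unrelated to timing. The noncentrality is 0.8 × √10 = 2.53 on 9 degrees of freedom, and the two-sided 5% test is significant about 62% of the time. A positive result there would not be evidence about timing.

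**The case against.** The strongest reply is that the plan already contains a natural check. LyE is itself primary, participants walk again on fresh data after the search, and the ANOVA compares conditions. A reader might infer from the SAP that nothing tests whether LyE depends on timing. The documents do not support that. In controls, four validation trials leave room for an optimised setting and at least one other suit setting, and an LyE contrast between them would test a timing effect at group level. What remains is that the plan does not say such a contrast exists, that it is unlikely in PAD with two trials, and that it would not show whether the optimum differs between people.

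Three other readings also go too far:

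- **That the timings are summarised only as mean ± SD, or are defined as optimal timings.** The SAP's descriptive list does not name them, and the primary-outcome sentence does not call them optimal; they could also describe the assistance delivered. What can be said is that no analysis specific to them is given.
- **That LyE is known to be noisy here, so that the percentages above predict this trial.** No repeatability figure is given. The percentages are conditional, and K = 10 represents PAD only.
- **That the mean timing is pulled toward the middle of the range.** This depends on the algorithm. With a true optimum at 0.80 and D = 1, 2 and 4, lowest-value picks average 0.62, 0.68 and 0.72, but a Gaussian-process search averages 0.72, 0.79 and 0.85, which at D = 4 overshoots away from the middle.

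**Conclusion.** The concern holds in a limited form. Two primary outcomes have no analysis of their own, and the generic summaries would report a timing, a between-person spread and a convergence count even if LyE did not depend on timing. That part follows from the design and needs only non-zero measurement error.

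The size under a real effect is not known. Under the assumptions above, the spread with no true differences between people is about 29% of the range on a flat surface, 23% at D = 2 and 20% at D = 4. It is smaller with a stronger signal or a modelled surface. The plan has no check of which case applies. The validation ANOVA may partly fill the gap in controls if it contrasts optimised with other timings. In PAD, if one trial is without the suit, it cannot. The change is worth making before analysis.

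**What to change.** Keep the mean ± SD as description and add an analysis of the two timings, by cohort:

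1. Fit LyE from all optimization conditions in a mixed-effects quadratic surface in measured extension and flexion timing, with participant effects and trial number.
2. Test the timing terms jointly against a flat surface. Because every evaluated setting is in the model, a likelihood-based fit can accommodate an adaptive search; in simulation the pooled test kept about 5% error under one.
3. Report the optimal timings with 95% confidence intervals from a bootstrap over participants.
4. Treat between-person variation of the optimum as exploratory. With an assumed 10 participants, 10 settings each and a true SD of 10% of the range, a test for it detected the variation in 9%, 28% and 85% of simulations at D = 1, 2 and 4.
5. If the timing terms are not significant, give the intervals and say that the data do not identify an optimum, not that none exists. Do not read the SD of chosen timings as evidence of individuality.

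The SAP should also name the suit conditions in the validation trials and the LyE contrasts to be tested.

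The cost is SAP wording and some analysis work, with no added walking or participants. The quadratic is an approximation. Power is low if the effect is weak: with an assumed 10 participants the joint test rejects in about 27% of simulations at D = 1 and 85% at D = 2. That is why step 5 is worded as a failure to identify an optimum.

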### Statistical analysis plan

Variability is quantified based on the Lyapunov Exponent. First, the optimal time lag (Tau) necessary for state-space reconstruction is estimated through the Average Mutual Information (AMI) algorithm. Tau is determined at the first local minimum of the AMI curve. Next, the optimal embedding dimension, representing the minimum number of variables required to accurately reconstruct gait dynamics, is determined using the False Nearest Neighbor (FNN) method. With these parameters (Tau and embedding dimension), the original gait time series are reconstructed into a multi-dimensional state space. LyE is computed using Wolf's algorithm, which evaluates how quickly neighboring trajectories in state-space diverge from each other. LyE is calculated individually for the hip, knee, and ankle joints.

Repeated-measures Analysis of Variance (ANOVA) is used to compare differences between conditions. The convergence of the optimization algorithm is statistically assessed by determining the number of assistance conditions after which the optimal exoskeleton settings no longer change as the convergence criterion.

Descriptive statistics are computed for all biomechanical variables, including joint angles, moments, and powers. Specifically, each biomechanical variable's mean and standard deviation are calculated across all participants for each experimental condition. These descriptive statistical values are consistently reported as mean  $\pm$  standard deviation. A significance threshold for all statistical tests is set at a p-value of 0.05.

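### The convergence rule, read as the last change of the optimum, gives every finite run a value, so unconverged runs are counted as converged and time to convergence is understated

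*Combined protocol and SAP*

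**What the plan says.** The Study protocol section lists "the time required for convergence of the optimization algorithm" among the primary outcome measures. The Statistical analysis plan gives it one sentence, which says "The convergence of the optimization algorithm is statistically assessed" and then defines the criterion as "determining the number of assistance conditions after which the optimal exoskeleton settings no longer change as the convergence criterion".

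The optimisation runs are finite: "healthy controls walk up to 20 minutes; patients with PAD walk 10x1 minutes with at least 2 minutes of rest". Of the optimiser, the protocol says only that it is guided by LyE and that "An algorithm prescribes the assistance profiles of the exoskeleton suit".

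The documents give no definition of the current optimum during a run, no tolerance for continuous settings, no required number of unchanged conditions, no category for runs that do not converge, and no rule for a change at the last condition. The plan also states "A significance threshold for all statistical tests is set at a p-value of 0.05", but names no test to which that threshold would apply for convergence.

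**The concern.** A time-to-event outcome needs a way to record that the event did not happen. Read as the last change, the SAP rule has none: a run still moving when walking ends receives a number just as a settled run does. Any summary then mixes the two and errs towards faster convergence.

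There is a second, softer problem. A reader may take a mid-run count as evidence that the algorithm located an optimum. LyE is an estimated quantity, and a search on noise also produces a last change. The plan gives nothing against which to judge the count. This matters because the study's stated aim is to evaluate optimisation methods, and this outcome describes how the method itself behaves.

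**Working it through.** The plan gives no expected count, number of conditions or sample size, so there is no figure to reproduce.

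**Inputs from the documents.** The rule and its primary status are as quoted above. Run length: "healthy controls walk up to 20 minutes" and "patients with PAD walk 10x1 minutes with at least 2 minutes of rest".

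**Assumptions.** n = 10 and n = 20 conditions, which would be one condition per walking minute. The optimiser and the ratio of signal to noise in LyE are also assumed.

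**Step 1, logic only.** Let c_k be the current optimum after condition k, and let L be the largest k at which c_k differs from c_(k-1), counting the first condition as a change. The set of such k is finite and not empty, so L always exists and 1 ≤ L ≤ n. If the optimum changes at the final condition, L = n. Had the run continued, its last change T could only have been at n or later. So n is a lower bound entered as an observed time, and the error is downward.

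**Step 2, the other reading.** The rule could mean stability over some later conditions. A run could then fail, but no window length is given, so this reading cannot be applied as written. Requiring one later unchanged condition removes only the runs with L = n.

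**Step 3, how many runs would have L = n.** For best-so-far search with each condition tried once in random order, the position of the lowest LyE is uniform on 1 to n, so P(L = n) = 1/n. The other rows are simulated.

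| Assumed optimiser | Signal | n = 10 | n = 20 |
|---|---|---|---|
| Best so far, random order | any | 10% | 5% |
| Quadratic surrogate | none | 29% | 22% |
| Quadratic surrogate | 2 SD | 17% | 11% |
| Gaussian process, two settings | none | 45% | 39% |
| Gaussian process, two settings | 2 SD | 36% | 18% |

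**Step 4, what the count says about signal.** For best-so-far search the mean is (n+1)/2: (10+1)/2 = 5.5 and (20+1)/2 = 10.5. Simulation gave the same for pure noise, a 4 SD signal and noise-free LyE. Mean L under other optimisers:

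| Assumed optimiser | n | No signal | With signal |
|---|---|---|---|
| Four revisited settings, lowest running mean | 10 | 5.61 | 4.90 (1 SD), 3.44 (2 SD) |
| Same | 20 | 11.6 | 8.1 (1 SD), 3.8 (2 SD) |
| Quadratic surrogate | 10 | 7.4 | 6.6 (2 SD), 5.5 (5 SD) |
| Quadratic surrogate | 20 | 14.6 | 12.2 (2 SD), 8.3 (5 SD) |
| Gaussian process | 10 | 8.7 | 8.4 (2 SD) |
| Gaussian process | 20 | 17.8 | 15.2 (2 SD) |
| Gradient type, gain 0.05 | 20 | 12.7 | 14.2 (1 SD) |

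In the gradient-type row, the mean distance to the optimum falls from 0.76 to 0.23, so the search succeeds while the count gets later. Another implementation of that optimiser gave 9.8 with no signal and 13.0 at 1 SD. The count can therefore be unrelated to signal, fall with it or rise with it.

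**Step 5, what a hold achieves.** Require the optimum to stay unchanged for three further conditions to the end of the run. Under best-so-far search, (n-3)/n of runs pass: 7/10 = 70% and 17/20 = 85%. With four revisited settings, 65% and 75% pass with no signal, and 92% and 99.5% at 2 SD. A hold creates a non-converged class, but it does not test for signal.

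**The case against.** The outcome is a measure of speed, and the plan states no hypothesis test on it. The planned mean and standard deviation are for biomechanical variables, so a mean of the count is not explicitly planned. An analyst would see L = n in the individual data. Whether the chosen setting helps is addressed by LyE and the validation trials. The random-order illustration fits poorly with an algorithm guided by LyE, and with strong signal and revisited settings the count behaves well. An upper limit of 20 minutes for controls also leaves room for an early-stopping rule, under which a run may end soon after it converges.

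Much of this stands, and it limits the point. It does not remove it. Seeing L = n is not the same as having a rule for it, and any summary of a primary outcome needs that rule. The possibility of early stopping means that a hold must not override the algorithm's own criterion.

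Two stronger readings are tempting. A reader might infer that the count is mere noise. The documents do not support this: no algorithm is named, and under several plausible ones the count carries information. A reader might also infer that convergence should be claimed only if it comes earlier than in a no-signal run. The gradient-type result shows that such a test could deny convergence where the search works.

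**Conclusion.** The point holds as a defect in the definition of a primary outcome and should be fixed. That every finite run receives a value, and that the error for unfinished runs is downward, follows from the last-change reading and needs no assumption about the optimiser. That the count does not by itself show a real optimum is supported by the illustrations, whose figures depend on the assumed n, optimiser and noise.

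Under those assumptions, between 5% and 45% of runs would still be changing at the final condition. This is a range over illustrations, not an estimate for this study. The documents support neither a claim that the study's convergence results will be wrong nor a claim that the rule is uninformative.

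**What to change.** In the SAP:

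1. Define the current optimum after each condition and, for continuous settings, a tolerance fixed before analysis. Count a run as converged only if the optimum stays unchanged or within tolerance for a pre-specified number of further conditions (for example three) to the end of the run, or if the algorithm's own pre-specified stopping rule was met. The value is the first condition of that stretch.
2. Report all other runs as not converged, right-censored at their last condition. Give the proportion converged, and summarise time to convergence with a method that handles censoring, such as a Kaplan-Meier median, rather than a plain mean. If too few runs converge for the median to be reached, say so.
3. Describe the count as the speed at which settings stabilise, and rest any claim of a true optimum on LyE in the validation trials. A no-signal run of the study's own algorithm may be shown as a descriptive reference, without a one-sided p < 0.05 condition on claiming convergence. If each condition is tried once in an order not driven by LyE, report the count as descriptive only.

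Also state the number of conditions and whether the unit is time or conditions; the protocol uses the first and the SAP the second.

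The cost is SAP wording, plus an offline run if the reference is wanted; no extra walking is needed. The optimum after each condition must have been kept, and the documents do not say whether it is. Some participants will be reported as not converged.
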